1.3. Nonclinical Studies

1.3.1. Pharmacologic Profile

An *in vitro* functional assay, MIN-117 showed a slight antagonist activity at 5-HT_{2B} receptor ($K_b=0.79\mu\text{M}$) and no agonist activity at 5-HT_{2B}.

MIN-117 inhibited monoamine uptake of the cells transfected with human recombinant transporters. Median inhibitory concentration (IC₅₀) values for the inhibiting effects of MIN-117 on 5-HT, norepinephrine and dopamine uptake are 6.0, 170 and 20 nmol/L, respectively. Reuptake inhibition of MIN-117 on 5-HT uptake was evaluated *in vivo* and compared with fluvoxamine, fluoxetine, and paroxetine of SSRI, venlafaxine of serotonin norepinephrine reuptake inhibitor (SNRI), and imipramine of tricyclic antidepressant (TCA). MIN-117 inhibited *ex vivo* binding to 5-HTT and 5-HT uptake and p-chloroamphetamine (PCA)-induced hyper-locomotion in rats at the dose range of 1-10 mg/kg, orally (PO) and the median effective dose (ED₅₀) values were 1.1, 7.1, and 1.7 mg/kg, PO, respectively.

The effects of MIN-117 on the release of the three main catecholamines, 5-HT, dopamine (DA) and norepinephrine (NE) were investigated in rats using microdialysis. Citalopram (10 mg/kg) was included as the reference compound of the SSRI type with clinically proven efficacy in patients with MDD. MIN-117 at the three tested doses induced modifications in the levels of the catecholamines. The findings showed no dose proportional effects. For the dose 0.1 mg/kg a very important increase in 5-HT (300%) and DA levels (235%) accompanied by some minor increases in the two metabolites dihydroxyphenylacetic acid (DOPAC) and Homovanillic acid (HVA) were observed. For the dose of 0.3 mg/kg an increase of 5-HT was observed (120%). For DA the observed increase was very important (270%) accompanied by some minor effects on DOPAC and HVA. An increase in NE levels could also be described at this dose (140%). For the dose of 3 mg/kg 5-HT levels increased (150%) concomitantly with a decrease of the serotonin metabolite 5-hydroxyindoleacetic acid (5-HIAA) levels.

1.3.2. Safety Pharmacology

The effects of MIN-117 on the general condition and behavior, central nervous system (CNS), respiratory and cardiovascular systems, digestive system, and water and electrolytes metabolisms were investigated. In *in vivo* experiments, MIN-117 was administered orally at doses of 1, 10, and 100 mg/kg, except that the rabbit orthostatic hypotension study employed intravenous doses of 0.1, 0.3, and 1 mg/kg and oral doses of 30, 100, and 300 mg/kg. As for *in vitro* experiments, MIN-117 was applied at concentrations of 3×10^{-7} , 3×10^{-6} , and 3×10^{-5} mol/L for measurements of action potential parameters in the isolated guinea pig papillary muscle and at 2×10^{-8} , 2×10^{-7} , and 2×10^{-6} mol/L for an ion channel assay (hERG or human ether-a-go-go-related gene).

MIN-117 at 1 mg/kg PO had no effects on general condition or behavior in rats. Decrease in spontaneous activity, suppression of reactivity, and narrowing of palpebral opening were observed at ≥ 10 mg/kg. Diarrhea was also observed at 100 mg/kg. All the noted changes disappeared within 24 hours after dosing.

MIN-117 at 1 mg/kg PO had no effect on the central nervous system in rats. Decrease in body temperature was noted at ≥ 10 mg/kg, and a decrease in spontaneous locomotor

activity and an inhibition of motor coordination at 100 mg/kg. There was no pro-convulsive effect at doses up to 100 mg/kg.

The telemetry study was conducted in conscious monkeys. MIN-117 increased heart rate at 100 mg/kg, but no effects on blood pressure or ECG parameters (PR interval, QRS duration, QT interval, or QTc) at doses up to 100 mg/kg. In the *in vitro* electrophysiology studies, MIN-117 blocked hERG channel (human I_{kr} channel expressed in CHO cells) at IC₅₀ of 0.43×10⁻⁶ mol/L. MIN-117 showed a prolongation of action potential duration in the isolated guinea pig papillary muscle preparations (5% prolongation for action potential duration at 90% (APD₉₀) compared to the pretreatment value) at the highest concentration of 3×10⁻⁵ mol/L. Effects on the orthostatic hypotension were evaluated by the head-up method in rabbits. There were no effects on any cardiovascular parameter by intravenous (IV) administration at doses up to 1 mg/kg. In the oral administration study, MIN-117 at 300 mg/kg decreased systolic and diastolic pressures after the recovery from tilting at 2, 8, 12, and 24 hours after dosing. At 100 mg/kg, low levels in diastolic pressure were also noted at 12 hours after dosing.

1.3.3. Toxicology

The toxicity of MIN-117 was characterized in rats and monkeys in oral single dose (1000 & 2000 mg/kg) and repeated dose studies (1, 3, 10, 30, 100, & 300 mg/kg) for up to 13 weeks duration.

At both doses in the single dose studies in rats, blepharoptosis was observed from 1 hour after dosing in both males and females; reddening of scrotum from 2 hours after dosing in males; and soiled perineal region from Day 1 in females. All the clinical signs disappeared by Day 10. Decreases in body weight gain were observed on Day 1 in both males and females, and continued to Day 7 in males at 2000 mg/kg.

At both doses in the single dose studies in monkeys, yellowish-white stool was observed in males and females from the day of dosing in the 2000 mg/kg group or from Day 2 in the 1000 mg/kg group and disappeared by Day 7. Increase of blood urea nitrogen (BUN) in males at both doses observed on Day 7.

At the 1000 mg/kg dose, vomiting was observed immediately after dosing in females. A decrease in triglycerides was observed in males and females and an increase of alanine aminotransferase (ALT) observed in males on Day 1. An increase in triglycerides was observed in males on Day 7.

At the 2000 mg/kg dose, soft stool was observed only on the dosing day in both males and females. Also observed was a decrease in food consumption on Day 1 and activated partial thromboplastin time (aPTT) prolongation on Day 13 in males. There was also an increase in triglycerides observed in males and females on Day 7.

In the 13-week (3, 10, 30, 100 mg/kg/day) rat study, 13 rats died or were sacrificed during the study: 8 males and 5 females at 100 mg/kg. Test article-changes in clinical signs, food consumption and body weight were only observed at 100 mg/kg/day: incomplete eyelid opening was sporadically observed until Day 7 of dosing; a decrease in body weight or suppression of body weight gain, together with a decrease in food consumption was noted from week 4; decrease in spontaneous activity and edema in the face, swelling in the extremities, and signs of deterioration were observed.

In the 13-week (3, 10, 100 and 300 mg/kg/day) monkey study, 5 monkeys died or were sacrificed during the study: 2 males and 2 females at 300 mg/kg, and 1 male at 100 mg/kg. Test article-changes in clinical signs, food consumption and body weight were observed from 100 mg/kg/day: increase in spontaneous activity for the first 2 weeks of dosing, stereotypy only at 300 mg/kg, decrease in spontaneous activity observed thereafter at 300 mg/kg and in monkey that died at 100 mg/kg; lateral position, disappearance of sound and touch response, decrease in papillary light reflex, hypothermia observed in monkeys that died or were sacrificed; soft stool, diarrhea, vomiting and emaciation; salivation observed in the latter half of the dosing in monkeys that survived at both doses; decreases in food consumption and body weight.

No lethal effect of MIN-117 was seen up to 30 mg/kg/day in rats and 10 mg/kg/day in monkeys in any of the repeated dose toxicity studies performed in both species. In the 13-week long-term toxicity studies, the No Observable Adverse Effect Level (NOAEL) was considered to be 3 mg/kg/day in rats, and 10 mg/kg/day in monkeys.

Reprotoxicity studies were performed in rats and rabbits. In rats, the NOAEL for maternal parameters was considered to be 30 mg/kg/day (corresponding to an AUC_{0-t} of 18540 ng.h/mL and a C_{max} of 850 ng/mL for MIN-117). The No Observed Effect Level (NOEL) for effects on embryo-fetal development was considered to be 30 mg/kg/day. In the pregnant rabbits after oral (gavage) administration of MIN-117 the NOAEL for maternal toxicity is therefore 5 mg/kg/day (corresponding to a mean AUC_{0-24h} of test item MIN-117 of 578 ng.h/m). There was no overt teratogenic potential of MIN-117. The NOAEL for embryo-foetal toxicity is therefore set at 45 mg/kg/day (corresponding to a mean AUC_{0-24h} of test item MIN-117 of 3449 ng.h/mL).

No genotoxic potential of MIN-117 was demonstrated in mutagenicity tests including the Bacterial reverse mutation tests in *Salmonella typhimurium* and *Escherichia coli* and the in vitro chromosomal aberration test with Chinese hamster lung cells; and the micronucleus test in mice and the in vivo/in vitro Unscheduled DNA Synthesis test in rat hepatocytes, where animals were adequately exposed to MIN-117.

1.3.4. Pharmacokinetic Profile

Pharmacokinetic studies of MIN-117 have been performed mainly in rats and monkeys.

After oral administration of ¹⁴C-MIN-117 in rats and monkeys, the plasma concentration of radioactivity reached C_{max} at 9.8 hours and 5.0 hours, respectively. It then declined with a terminal elimination half-life (t_{1/2}) (12 to 72 hours) of 19.9 hours in rats and 20.7 hours in monkeys and t_{1/2} (72 h-t) of 33.2 hours in rats and 50.1 hours in monkeys (t: last quantifiable time point). The absorption rate estimated by dividing AUC_{0-∞, PO} by AUC_{0-∞, IV} was 85.3% for rats and 73.3% for monkeys.

The plasma concentration of unchanged MIN-117, detected after oral administration of MIN-117 in rats, reached the maximum level (C_{max}) at 6.0-6.8 h and then declined with a t_{1/2} of 8.8 to 9.6 hours. The bioavailabilities (F) at 0.3, 1, and 3 mg/kg were 81.3, 95.5, and 95.2%, respectively. After intravenous administration at a dose of 1 mg/kg, total clearance (CL) and volume of distribution at steady state (V_{ss}) were 1.15 L/h/kg and 10.04 L/kg, respectively. In monkeys, the plasma concentration of unchanged MIN-117 reached C_{max} at 1.0 to 1.5 hours and then declined with a t_{1/2} of 3.0 to 6.8 hours. F at 0.3, 1, and 3 mg/kg

were 14.4, 14.6, and 12.3%, respectively and after intravenous administration at a dose of 1 mg/kg, CL and V_{ss} were 0.78 L/h/kg and 2.40 L/kg, respectively.

Following a single oral administration to male rats, the tissue concentration of radioactivity reached the peak level at 3 hours after administration in thyroid gland, trachea, liver, stomach and small intestine and at 7 to 12 hours after administration in the other tissues. In almost all the tissues, the concentration of radioactivity was higher than that in plasma. At 3 to 24 hours after administration, relatively higher levels of radioactivity are detected in harderian gland, liver, lung, adrenal gland, pancreas, pituitary gland, fat and brown fat except gastro-intestinal tissues. At 168 hours after administration, the radioactivity concentration in all of the tissues was declined to 2% or less of the maximum concentration. Following repeated oral administration rats, mostly all radioactivity concentrations in the tissues reached their maxima at 7 h after administration on Day 1 and after 7, 14, and 21 days of administration, and declined after single, 7 days, 14 days, and 21 days of administration to 0%, 4% or less, 16% or less and 18% or less (33% or less for females) of their maxima at 168h post-dosing respectively.

Finally distribution rate of radioactivity in blood cells was 33.8% to 42.9% in rats, 8.6% to 12.2% in monkeys, and 2.1% to 9.6% in humans. The plasma protein binding rate of ^{14}C -labeled MIN-117 or unlabeled MIN-117 was 82.3 to 96.1% in rats, and over 96.5% in monkeys and humans. The protein binding rate was over 99.6% in human serum albumin, 84.4% in human γ -globulin, and 97.1% in human α 1-acid glycoprotein.

The major route of elimination of radioactivity was fecal excretion via the bile. The excretion rates in feces of radioactivity of the dose after oral administration were 78.3% in rats and 65.2% in monkeys up to 168 hours. The enterohepatic circulation rate was 50.2% in rats.

1.3.5. Behavioral and Pharmacodynamics Studies

MIN-117 was tested in four kinds of animal models to evaluate its antidepressant effects. Successive oral administration of MIN-117 0.3 mg/kg for 3 days completely reversed the locomotor activities reduced by the handling stress in F344 rats. In this model, fluoxetine, venlafaxine and imipramine also reversed the motor activity, but the onset of these drugs was prominently slower than that of MIN-117. MIN-117 also reversed sucrose consumption of rats in the depression model of chronic mild stress (CMS). The magnitude of action of the most active doses of MIN-117 (0.001 and 1.0 mg/kg) was comparable to that of imipramine (10 mg/kg); by the end-of-treatment period the sucrose consumption in stressed animals treated with these doses was restored to the pre-stress level. The onset of action of these doses was clearly faster than that of imipramine; the enhancement of sucrose intakes reached statistical significance already following the first week of administration, compared to four weeks required by imipramine. The CMS procedure decreased the recognition index measured in the Novel Object recognition test. In stressed animals MIN-117, administered at doses of 0.001, 0.01 and 0.1 mg/kg, restored the recognition index to the level of the vehicle- or drug-treated control animals, while Imipramine was ineffective.

In the forced swimming test, MIN-117 shortened the immobility time with an ED_{50} of 15 mg/kg PO. In the marble burying (MB) test, results showed that MIN-117 suppresses the MB behavior without affecting locomotor activity in mice.

The reinforcing effect of MIN-117 was investigated in the self-administration experiment in monkeys. Results suggested that MIN-117 possessed a reinforcing effect but of very weak intensity considered compared to that of cocaine.

MIN-117 was tested in order to evaluate potential sexual side effects following acute (1 day), subchronic (7 days) and chronic (14 days) of treatment in a model of sexual dysfunction in rats. The serotonin reuptake inhibitor (SSRI) compounds Paroxetine Hydrochloride (10 mg/kg) and Citalopram (10 mg/kg) were used as reference compounds as SSRIs have a known inhibitory effect on the display of male sexual behavior. In the study, the SSRI reference compounds, Citalopram and Paroxetine, decrease sexual performance as measured by different parameters (increased latencies to display the first mount and the first ejaculation, slight reduction in the total number of ejaculations). MIN-117 had a significant effect to decrease the latency to display the first mount attempt. The dose of 0.03 mg/kg displayed a significant increase in number of mount attempts compared to vehicle group. The MIN-117 compound had no significant effect on the number of intromissions displayed by male rats, nor in the total number of ejaculations.

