1.2. MIN-117 Pharmacological Profile and Rationale as a Unique Antidepressant

MIN-117 is an investigational antidepressant belonging to a new chemical class, the benzofuran derivatives. The chemical designation is (2*S*)-1-[4-(3,4-Dichlorophenyl)piperidin-1-yl]-3-[2-(5-methyl-1,3,4-oxadiazol-2-yl)benzo[*b*]furan-4-yloxy]propan-2-ol monohydrochloride. MIN-117 is characterized by its affinity for 5-HT_{1A} pre-synaptic autoreceptors and 5-hydroxytryptamine transporters (5-HTT). The K_i values for 5-HT_{1A} receptors and 5-HTT of human were 5.0 and 0.81 nmol/L, respectively. MIN-117 acts as a serotonin reuptake inhibitor. In addition, MIN-117 has high affinity for adrenergic alpha (α)₁ and serotonergic 5-HT_{2A} and acts as antagonist to each receptor. MIN-117 is also active as a dopamine transport (DAT), by inhibiting reuptake of dopamine from the synaptic cleft. Furthermore, MIN-117 has moderate affinity for 5-HT_{2C} and also acts as a moderate norepinephrine transporter (NET) inhibitor.

For the most accurate and current information regarding the efficacy and safety of MIN-117, refer to the latest version of the Investigator's Brochure for MIN-117.

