In the SON-117-C01 study, 132 TEAEs were reported (40 with placebo, 40 with MIN-117 1 mg, 22 with MIN-117 3 mg and 30 with MIN-117 7.5 mg). The body systems most frequently affected were the Nervous system (36), Skin and subcutaneous system (26), and Gastrointestinal system (23). The most frequently reported TEAEs were headache (15 episodes: 7 with placebo, 1 with MIN-117 1 mg, 2 with MIN-117 3 mg and 5 with MIN-117 7.5 mg dose) and insomnia (10 episodes; 5 with placebo, 2 with 1 mg dose, 1 with 3 mg dose and 2 with 7.5 mg dose). All TEAEs were mild or moderate in intensity. Only 1 TEAE was rated as severe (fatigue, MIN-117 7.5 mg).

Among the reported TEAE, 62 were considered related to the study drug: 22 with placebo (66.7% of the subjects) and 40 with MIN-117: 22 with MIN-117 1 mg (60% of the subjects); 8 with MIN-117 3 mg (40% of the subjects) and 10 with MIN-117 7.5 mg (44% of the subjects).

The most frequently reported ADRs were insomnia (9 episodes: 5 with placebo, 1 with MIN-117 1 mg; 1 with MIN-117 3 mg and 2 with MIN-117 7.5 mg), headache (6 episodes: 5 with placebo and 1 with MIN-117 1 mg) and diarrhea (5 episodes: 2 with placebo, 2 with MIN-117 1 mg and 1 with MIN-117 7.5 mg).

Of note, in the SON-117-C01 study, escitalopram was administered as a positive control to 9 subjects. In this group, 28 ADRs were reported (88.9% of the subjects). The most frequently reported ADRs were asthenia (5 episodes) and headache (3 episodes).

Results on the SSRI withdrawal scale indicated that there were no more self-perceived adverse events with MIN-117 than with placebo or escitalopram.

No significant biological abnormalities were evidently related to MIN-117.

Repeated doses of MIN-117 induced no clinically relevant changes in blood pressure. All mean values of supine systolic and diastolic blood pressure as well as heart rate were within the normal range. There was a trend toward a slight decrease in supine DBP with MIN-117 3 mg (Day 1, Day 14 and Day 18) when compared to placebo. The incidence of abnormal orthostatic tests was also higher with MIN-117 3 mg, although none of them were symptomatic. Heart rate tended to increase following MIN-117 3 mg administration. This

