Post-Study Visit: At the end of the study, patients will be evaluated for safety/tolerability at the Post-Study Visit, approximately 2 weeks after completing the Double-blind Treatment Phase. Any patient who terminates from the study early will undergo the Early Withdrawal visit procedures and will have a Post-Study Visit within approximately 2 weeks.

Figure 1: Study Design Diagram (Timelines not to scale)

Study Evaluations

The primary efficacy endpoint will be the change in MADRS total score from Baseline (i.e., the start of double-blind treatment) to the end of the double-blind treatment period (i.e., Week 6). Secondary and exploratory efficacy evaluations include the: HAM-A, CGI-S, CGI-I, IDS-SR₃₀, SHAPS, DSST, PSS, A-SEX, and sleep parameters as assessed by Somno-Art, at specified time-points as outlined in the [Time and Events Schedule](#).

Blood samples (6 mL) for assessing MIN-117 concentration in plasma will be obtained at Baseline (Visit 2), during the double-blind period at Weeks 2, 4, and 6 (Visits 3, 4, and 5), and during the Post-Study Visit (Visit 6). Samples will be taken at pre-dose (within 1 hour) and approximately 2 to 4 hours after dosing (C_{max}) at Baseline (Visit 2) and Weeks 2, 4, and 6 (Visits 3, 4 and 5). Only 1 sample will be taken at the Post-Study Visit (Visit 6).

Blood samples will be collected for pharmacodynamic assessment of BDNF, GDNF, VEGF, IGF-1, fibroblast growth factor-2, C-reactive protein, cortisol, amyloid-A, IL-1 β , IL-6, and IL-10 at Baseline and the Week 6 visit.

A pharmacogenomic blood sample will be obtained (at sites where local regulations permit) at Visit 2 or later to allow for pharmacogenomic research, as necessary. Patients will also be asked for consent for storage of their DNA sample for future research.

Safety will be assessed by monitoring adverse events, clinical laboratory tests (including hematology, serum chemistry, urinalysis, lipid profile, and pregnancy tests), vital sign assessments, physical and neurologic examinations, and ECGs. Suicidal ideation/behavior will be assessed using the C-SSRS.

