10.8.1. Adverse Events

The original terms used in the eCRFs by investigators to identify adverse events will be coded using the Medical Dictionary for Regulatory Activities (MedDRA). All reported adverse events with onset during the 6-week double-blind period (i.e., treatment-emergent adverse events or TEAE) will be included in the analysis. For each adverse event, the percentage of patients who experienced at least one occurrence of the given event will be summarized by treatment group.

Special attention will be given to those patients who died, or who discontinued treatment due to an adverse event, or who experienced a severe or a serious adverse event (e.g., summaries, listings, and narrative preparation may be provided, as appropriate).

A TEAE that occurs > 14 days after the date of the last dose of double-blind treatment will not be summarized.

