11.2. Special Reporting Situations

Safety events of interest on a sponsor study drug that may require expedited reporting and/or safety evaluation include, but are not limited to:

- Overdose of a sponsor study drug.
- Suspected abuse/misuse of a sponsor study drug, defined as 3 x daily dose within any 24-hour period.
- Accidental or occupational exposure to a sponsor study drug.
- Medication error involving a sponsor product (with or without patient/patient exposure to the sponsor study drug, e.g., name confusion).
- Exposure to a sponsor study drug during pregnancy or breastfeeding.

Special reporting situations should be recorded in the eCRF. Any special reporting situation that meets the criteria of a SAE should be recorded on the SAE page of the eCRF.

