Any recorded Adverse Event that occurs on or after the initiation of study treatment is considered treatment-emergent (TE). Additionally, it is assumed that an Adverse Event which was reported to have started on Day 1 without an associated onset time may have occurred after the initiation study treatment. Hence, Adverse Events occurring on Day 1 without an onset time are assumed to be TE.

Concomitant Medications

Concomitant medications are those medications taken on or after the initiation of study treatment. This definition includes medications started prior to the initiation of study treatment, but continuing concomitantly with study treatment.

Prior Medications

Prior medications are those medications taken and completed prior to the initiation of study treatment.

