5.4. SAFETY ANALYSES

5.4.1. Adverse Events

Adverse events will be mapped to a Medical Dictionary for Regulatory Activities (MedDRA) version 21.0 preferred term and system organ classification. If a patient experiences multiple events that map to a single preferred term, the greatest severity grade and strongest investigator assessment of relation to study medication will be assigned to the preferred term for the appropriate summaries. Should an event have a missing severity or relationship, it will be classified as having the highest severity and/or strongest relationship to study medication.

The occurrence of TE adverse events (TEAEs) will be summarized by treatment group using preferred terms, system organ classifications, and severity. Separate summaries of TE serious adverse events (SAE), TEAE related to study treatment, TEAE leading to discontinuation of study treatment, and TE fatal adverse events will be generated. All adverse events reported will be listed for individual patients showing both verbatim and preferred terms, as well as system organ class. All adverse events that occurred prior to the

initiation of study treatment will be excluded from the tables but will be included in the listings. Any TEAE occurring after the End of Study visit will not be summarized.

Missing onset dates will be imputed as previously outlined in Section 3.3.5 as required to determine TE events. Adverse events occurring on Day 1 with missing onset times will be assumed to be TE.

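### The planned TEAE tables pool events that start in the roughly two dose-free weeks with on-treatment events, and the protocol and SAP do not agree on where the TEAE window ends

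*Protocol*

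**What the plan says.** **Start of the TEAE window.** SAP 3.3.8: "Any recorded Adverse Event that occurs on or after the initiation of study treatment is considered treatment-emergent (TE"). No end at the last dose is given.

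**End of the window.** SAP 5.4.1: "Any TEAE occurring after the End of Study visit will not be summarized". Protocol 10.8.1 opens differently: "All reported adverse events with onset during the 6-week double-blind period (i.e., treatment-emergent adverse events or TEAE) will be included in the analysis". The same section then says that a TEAE more than 14 days after the last dose will not be summarized. SAP Section 7 lists no change from the planned analysis.

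**Follow-up.** Protocol Section 3: "patients will be evaluated for safety/tolerability at the Post-Study Visit, approximately 2 weeks after completing the Double-blind Treatment Phase". The schedule puts the last treatment visit at Day 43 and follow-up at Day 57. Early withdrawers also return about 2 weeks later.

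**Outputs.** SAP Section 9 lists AE tables 14.3.1.1 to 14.3.1.5 and 14.3.2.1. None separates events that begin after the last dose.

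**Background.** Protocol 1.2: "MIN-117 acts as a serotonin reuptake inhibitor". The schedule has no withdrawal scale. An earlier 14-day study in healthy subjects used one (Protocol 1.4, safety results of SON-117-C01): "Results on the SSRI withdrawal scale indicated that there were no more self-perceived adverse events with MIN-117 than with placebo or escitalopram".

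**Special situations.** Protocol 11.2 covers overdose, suspected abuse or misuse, and medication error: "Special reporting situations should be recorded in the eCRF". SAP Section 9 names no table or listing for them. Protocol 1.3.5, on self-administration in monkeys: "Results suggested that MIN-117 possessed a reinforcing effect but of very weak intensity considered compared to that of cocaine".

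**The concern.** A TEAE table is normally read as what happens to patients while they take the drug. Here it also contains what happens after they stop. If stopping MIN-117 produces symptoms, two things follow. The excess appears in the pooled table and is read as an on-treatment effect. And the timing, which is what would identify it as a post-stopping effect, is not displayed by arm.

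This trial plans about 162 patients on MIN-117 against 162 on placebo. In the completed phase 2a study, 21 patients received 2.5 mg for up to 6 weeks. The present trial is therefore a much larger controlled look at stopping the drug, and the plan does not tabulate that look.

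Separately, the end of the window is unsettled. Depending on which sentence is followed, post-dose events are all out, in up to a fixed day, or in up to a visit.

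**Working it through.** The point disputes no stated figure. The arm sizes used below come from the sample-size section and do reproduce: a difference of 4, SD 9 and two-sided alpha 0.025 with 146 versus 73 give 79.99% power by the noncentral t. Inflation gives 146/0.9 = 162.2 and 73/0.9 = 81.1, stated as 162 and 81.

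**1. Share of the window after the last dose.** Day 1 to Day 57 is 56 days; Day 43 to Day 57 is 14. 14/56 = 25%. For a patient whose last dose is on Day 15 and who returns 14 days later, it is 14/28 = 50%. The mix of on-dose and off-dose time therefore depends on dropout, which may differ by arm.

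**2. The cut-offs side by side.** Visits 5 and 6 each have a ±3-day window relative to Baseline, so Visit 5 falls on Days 40–46 and Visit 6 on Days 54–60. The gap runs from 54 − 46 = 8 days to 60 − 40 = 20 days.

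| Text | Post-dose events summarized |
|---|---|
| Protocol 10.8.1, first rule | none |
| Protocol 10.8.1, last rule | up to day 14 after last dose |
| SAP 5.4.1 | up to Visit 6: day 8 to day 20 for completers dosed up to Visit 5 |

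At nominal timing the last two coincide (43 + 14 = 57). Off nominal they do not, and neither matches the first.

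**3. Drug remaining after the last dose.** Fraction = 0.5^(24d/t½). Protocol 1.4.1 gives a terminal half-life of 50–60 h after multiple doses.

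- Day 3: 37–44%
- Day 7: 10–14%
- Day 14: 1–2%

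The same sentence also carries a range of 82–105 h. What that range refers to is not clear from the public text; if it applied, 6–11% would remain at day 14. The interval is dose-free, not drug-free. At 50–60 h it covers the washout, since 5 half-lives take 10.4–12.5 days.

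**4. What pooling does to a by-arm contrast.** The documents give no post-dose event rates, so all rates here are assumptions. Let b be the on-treatment incidence of a symptom, equal in both arms, and w the post-dose incidence, independent of it. The pooled rate is 1 − (1 − b)(1 − w), so the pooled difference is (1 − b)(w₁ − w₀). Power is the two-sided 0.05 normal approximation with pooled null variance, at 162 versus 162. The plan tests no AE rates; power only gauges how visible a difference is.

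| Post-dose, placebo vs MIN-117 | Separate table | b = 5% | 10% | 15% | 20% |
|---|---|---|---|---|---|
| 2% vs 10% | 86% | 60% | 43% | 33% | 27% |
| 5% vs 15% | 85% | 68% | 54% | 44% | 36% |
| 5% vs 10% | 40% | 26% | 19% | 15% | 13% |

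Example: for 2% versus 10% with b = 10%, the pooled rates are 1 − 0.90 × 0.98 = 11.8% and 1 − 0.90 × 0.90 = 19.0%, a difference of 7.2 points. Most of the difference survives, but it sits on a larger background and carries no timing. For scale, dizziness and headache were each reported in 8.5% of patients across all arms of the earlier MDD study.

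For one dose (81 versus 162), the separate table has 75%, 73% and 33% power for the three rows.

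**5. Special situations.** The chance of at least one case among 162 MIN-117 patients is 1 − (1 − p)^162: 56% at p = 0.5%, 80% at 1% and 96% at 2%.

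**The case against.** A reader might infer that the trial cannot show withdrawal or abuse signals, that post-dose AE onset is its only evidence on stopping, or that abuse and misuse are never tabulated. The documents do not support any of these.

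- All AEs are listed per patient, and SAP Section 5 sorts listings by treatment group, patient and date. A split could be made later from the same data.
- C-SSRS, vital signs, ECG and laboratory tests are collected at Visit 6 and summarized by visit or time point and arm (SAP 5.4.2, 5.4.4).
- Special situations that are serious go to the SAE page and can reach table 14.3.2.1. Those also reported as AEs enter the TEAE tables. Compliance is summarized by arm with its maximum (SAP 5 and 5.1), so overuse in an arm would show there. Only non-serious cases not reported as AEs lack a planned table.

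It is also fair to say that the SAP follows one of the protocol's own two rules at nominal timing. The earlier withdrawal-scale result was null in a study that included 7.5 mg, and no objective of this trial concerns withdrawal or abuse liability. Calling every post-dose event withdrawal would mislabel effects of drug still present.

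All of this stands, and it limits the point to table layout and definition. It does not remove it. Patient listings are not a by-arm comparison, and a split first chosen after unblinding is post hoc. The null withdrawal-scale result comes from 29 healthy men on MIN-117 dosed for 14 days, not from patients stopping after 6 weeks.

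**Conclusion.** The point holds as a gap in the planned tables and an inconsistency in the TEAE window. It is not a limit on what the data can show. About 25% of the nominal window is post-dose and is not displayed separately. Protocol 10.8.1 contradicts itself, and the SAP uses a third, visit-based end-point that can differ from the 14-day rule by up to 6 days in either direction.

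Under the assumed rates, pooling lowers power from about 86% to 27–60% (2% versus 10%) or from 85% to 36–68% (5% versus 15%). It dilutes a signal and does not erase it. These figures rest on equal on-treatment rates in both arms and on independence between periods. For a smaller effect such as 5% versus 10%, even a separate table has only about 40% power, so it would be descriptive.

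The monkey finding, very weak by the protocol's own account, is background and does not carry this conclusion.

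**What to change.** 1. Reconcile the TEAE end-point: one rule, stated identically in Protocol 10.8.1, SAP 3.3.8 and SAP 5.4.1.
2. In SAP 5.4.1 and Section 9, present TEAEs by arm and preferred term overall and split by onset: (a) first dose to last dose; (b) after last dose to Visit 6. Label (b) *post-treatment onset*, not withdrawal, because 10–14% of drug remains at day 7 at a 50–60 h half-life.
3. State how partial onset dates are allocated between (a) and (b). SAP 3.3.5 imputes from Day 1, which serves the start of the window and not the split.
4. Optional and secondary: a by-arm count or named listing of special reporting situations.

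The cost is wording and a few table shells, from data already collected. Conduct, sample size and efficacy alpha are unaffected. The downside is low counts and limited power in (b), which the table should acknowledge.
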